	
in distance-corrected near visual acuity (DCNVA) compared to Placebo-treated subjects, with a trend for a 2-line improvement at all timepoints. In these studies, Nyxol was generally well tolerated in the eye (most common complaint was mild-to-moderate ocular hyperemia) and there were no clinically meaningful systemic effects, as measured by heart rate (HR) and blood pressure (BP).

Study Objectives	
The objectives of this study are:
 

• To evaluate the efficacy of Nyxol + LDP to improve DCNVA compared to Placebo alone in subjects with presbyopia

• To evaluate the efficacy of Nyxol + LDP to prevent < 1 line of loss of BCDVA

• To evaluate the efficacy of Nyxol + LDP to improve DCNVA compared to Nyxol alone or LDP alone

• To evaluate the ability of Nyxol + LDP to produce the “pinhole” pupil size (approximately 1.6-2 mm)

• To evaluate the efficacy of Nyxol + LDP to improve BCIVA and BCDVA

• To evaluate the effect of iris color on the efficacy of Nyxol + LDP

• To evaluate the ocular and systemic safety of Nyxol + LDP and each component individually

 
The Sponsor intends to use this Phase 2 study to evaluate Nyxol + LDP for the chronic indication of “temporary treatment of presbyopia.”

Design	
This is a placebo-controlled, double-masked, multiple-dose, Phase 2 study in approximately 152 randomized subjects with presbyopia (approximately 140 evaluable for efficacy), evaluated for safety and efficacy following administration of masked Nyxol or Placebo (Treatment 1) at or near bedtime for 3 to 4 days, with administration of LDP or No Treatment (Treatment 2) at the next visit (Visit 2) in the morning. Measurements will be made at multiple visits and timepoints, and analysis will consist of comparison across 4 treatment arms:
 

• Nyxol + LDP

• Nyxol + No Treatment 2 (Nyxol alone)

• Placebo + LDP

• Placebo + No Treatment 2 (Placebo alone)

 
Subjects will be randomized 4:3:3:4 into the above groups. Randomization will be stratified 1:1 by iris color.

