4.1. Study Objectives

The objectives of this study are as follows:

Primary objective

- To evaluate the efficacy of Nyxol + LDP to improve distance-corrected near visual acuity (DCNVA) compared to Placebo alone in subjects with presbyopia

Secondary objectives

- To evaluate the efficacy of Nyxol + LDP to prevent >1 line of loss of best-corrected distance visual acuity (BCDVA)
- To evaluate the efficacy of Nyxol + LDP to improve DCNVA compared to Nyxol alone or LDP alone
- To evaluate the ability of Nyxol + LDP to produce the “pinhole” pupil size (approximately 1.6-2 mm)
- To evaluate the efficacy of Nyxol + LDP to improve distance-corrected intermediate visual acuity (DCIVA) and BCDVA
- To evaluate the effect of iris color on the efficacy of Nyxol + LDP
- To evaluate the ocular and systemic safety of Nyxol + LDP and each component individually

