5.3. Randomization and Masking

A randomization code for allocating subjects to treatment will be prepared by a masked biostatistician not connected with the study. At the initiation of study-related procedures, every subject who is screened is assigned a subject number within numerical order within each site. Once a subject is qualified for the study, the subject is assigned a randomization number in the order provided by the biostatistician.

[figure not shown]
Subjects will be then randomized 4:3:3:4 into 1 of 4 treatment arms:

- Nyxol + LDP
- Nyxol + No Treatment 2 (Nyxol alone)
- Placebo + LDP (LDP alone)
- Placebo + No Treatment 2 (Placebo alone)

Randomization will be stratified 1:1 by iris color (light/dark irides).

A randomization schema for evaluable subjects by investigational treatment (Treatment 1 and Treatment 2) and irides type is described in Figure 1.

Figure 1 **Randomization schema by investigational treatment and irides type**

The Treatment 1 study medications will be masked to Investigators, Site Staff, study subjects, Ocuphire, and all other study personnel involved in the conduct of the study. Only in case of medical emergency or occurrence of SAEs will the randomization code be unmasked by the Medical Monitor and made available to the Investigator, Ocuphire, and/or other personnel involved in the monitoring or conduct of this study.

Treatment 2 (LDP or No Treatment) is unmasked and will be administered on Visit 2 by a designated, unmasked, Site Staff member, distinct from the Site Staff member recording measurements/assessments.

Randomization for both Treatments will occur at Visit 1.

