7.1.2. Per Protocol Population (PP)

The PP population included all subjects in the mITT population who received one drop of Treatment 1 the day prior to Visit 2 and were administered Treatment 2 at Visit 2, had binocular DCNVA and BCDVA in photopic conditions at Baseline (Visit 1) and at Visit 2 time 1 hour, and had no major protocol deviations. The PP population will be used for the primary endpoint analysis and to analyze all efficacy endpoints, with subjects included in their randomized treatment regardless of the treatment they actually received.

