7.2.2. Planned Subgroups

Subgroup analyses by irides type (light, dark) will be completed for efficacy endpoints.

Other possible subgroups include age, sex, and race.

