9.1.1. Primary Efficacy Analysis

The primary efficacy endpoint is the percent of subjects with ≥ 15 letters of improvement in photopic binocular DCNVA on Visit 2 at 1 hour with Nyxol + LDP compared to Placebo alone in the study eye. If the analysis using the PP Population shows a positive effect for Nyxol at the 0.05 level of significance, the primary endpoint will be considered met. The primary efficacy endpoint will be analyzed using a logistic regression model with treatment and light/dark irides as factors and the baseline DCNVA as a covariate. The percentage of subjects in each treatment group meeting the criteria, the odds ratio (OR) with 95% CI, and p-value will be provided. Example SAS code is as follows:

[REDACTED]

By including irides type as a factor in the primary efficacy analysis model, the model efficiency as well as a change in the treatment effect will be increased. Including this factor in the model will also make the results more generalizable to other studies in which the sample characteristics may differ from the current study [2].

In addition, the primary efficacy endpoint will be analyzed by light/dark irides using the same model indicated above but without irides as a factor. For this subgroup analyses, observed case data only will be used; that is, missing values will not be imputed.

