9.1.2. Secondary Efficacy Analyses

Secondary efficacy endpoints are indicated in Section 4.2.2. Secondary efficacy endpoints will be analyzed by study eye, fellow eye, and binocular (if available) using the PP population, and the mITT population for selected endpoints (see the list of planned tables, Section 12.1, for details).

All continuous secondary endpoints derived from VA assessments, such as change in DCNVA, DCIVA, and BCDVA, will be analyzed using Early Treatment Diabetic Retinopathy Study (ETDRS) letters correctly read. Any secondary endpoints using Snellen measurements will be converted from letters read as follows:

Table 2 Snellen Equivalents to VA Assessment Letters Read

DCNVA/DCIVA letters	Snellen	BCDVA letters
≥75	20/15	≥60
70 - 74	20/20	55 - 59
65 - 69	20/25	50 - 54
60 - 64	20/32	45 - 49
55 - 59	20/40	40 - 44
50 - 54	20/50	35 - 39
45 - 49	20/63	30 - 34
40 - 44	20/80	25 - 29
35 - 39	20/100	20 - 24
30 - 34	20/125	15 - 19
25 - 29	20/160	10 - 14
<25	20/200	<10

Each of the continuous secondary efficacy endpoints will be analyzed using analysis of covariance (ANCOVA), with observed value as the dependent variable, treatment, and light/dark irides as factors, and the respective baseline value included as the covariate. Another ANCOVA will be applied with change from baseline as the dependent variable using the same factors and covariates.

The output from each ANCOVA will include the LSM and SE for all treatment groups, along with each LSM, the 95% CI and associated p-value for Nyxol + LDP vs. Nyxol alone, Placebo + LDP, and Placebo alone. Continuous pupil diameter endpoints will be assessed using the study eye, fellow eye, and best eye, which is defined as the eye with the greatest reduction in diameter.

For each of the secondary endpoints related to percent of subjects achieving certain criteria, the analysis will be performed using a logistic regression model with treatment and light/dark irides as factors, and the respective baseline as a covariate. For each analysis, the percentage of subjects in each treatment group meeting the criteria will be presented, and the OR with 95% CI and p-value will be provided for Nyxol + LDP vs. Nyxol alone, Placebo + LDP, and Placebo alone. Categorical pupil diameter endpoints will be assessed using the study eye, fellow eye, and either eye, which is defined as achieving a given criterion in either eye.

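### For its secondary objective on iris colour, the readable SAP plans separate light and dark analyses but no prespecified estimate, with CI, of how the treatment effect differs between them

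*SAP*

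**What the plan says.** SAP 4.1 lists as a secondary objective "To evaluate the effect of iris color on the efficacy of Nyxol + LDP", and Protocol 3 has the same objective. Iris colour is also the stratification factor: "Randomization will be stratified 1:1 by iris color" (Protocol 1; likewise Protocol 4.6 and SAP 5.3).

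The readable analysis text that bears on this objective is:

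- **SAP 7.2.2:** "Subgroup analyses by irides type (light, dark) will be completed for efficacy endpoints".
- **SAP 9.1.1, primary endpoint:** "the primary efficacy endpoint will be analyzed by light/dark irides using the same model indicated above but without irides as a factor". It adds: "For this subgroup analyses, observed case data only will be used; that is, missing values will not be imputed".
- **SAP 9.1.2, secondary endpoints:** the overall responder models use "treatment and light/dark irides as factors, and the respective baseline as a covariate". The ANCOVA models have the same terms. Each endpoint is then refitted by iris group with the irides factor dropped.
- **SAP 7.2.1:** the only planned covariates are baseline values.
- **SAP 7.4.1:** p-values for secondary efficacy endpoints are descriptive.

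The example SAS code in SAP 9.1.1, the table list in SAP 12.1 and the primary-model terms in Protocol 9.3.5 are redacted.

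**The concern.** The natural reading of the objective is effect modification: is the benefit of Nyxol + LDP over Placebo alone larger or smaller in dark than in light irides? A main effect for irides adjusts for iris colour but imposes one common treatment effect. The reasons SAP 9.1.1 gives for including the factor are efficiency and generalizability, not effect modification. Separate refits give two effects side by side, but neither states the difference between them or its uncertainty.

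Without a prespecified contrast, the objective may be answered informally by noting which stratum reaches p ≤ 0.05, or by a contrast whose scale, endpoint and population are chosen after unmasking. The overall primary conclusion is not at stake. What is missing is a planned number that matches a stated objective.

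**Working it through.** **1. Is there a contrast anywhere in the readable text?** In the SAP sections listed above and in Protocol 7.1 and 9.3.5, every iris analysis is either a within-stratum refit or a main-effect adjustment. No treatment-by-irides term, interaction test, difference of effects or ratio of effects is named.

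**2. Sample size per cell.** SAP 6 gives 140 evaluable subjects allocated 4:3:3:4, so 140 × 4/14 = 40 in each primary arm, as stated. Allowing for 7% drop-out, 140/0.93 = 150.5, consistent with the stated figure of about 152. The power and response rates in Protocol 9.1 are redacted and cannot be reproduced. *Assumption:* 1:1 stratification means equal iris strata, so 40/2 = 20 per arm per stratum. SAP Figure 1, which may show the split, is not in the available text, and the PP set may be smaller.

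**3. Precision of a continuous contrast** (in units of residual SD).

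- Overall effect: 1.96 × √(2/40) = 0.44.
- Difference between two stratum effects: 1.96 × √(4/20) = 0.88, twice as wide.
- With 38 per arm (Protocol 9.1), so 19 per cell: 1.96 × √(4/19) = 0.90.

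**4. Precision of the ratio of odds ratios** (assumed response rates). The large-sample SE of the log ratio is √2 × √[1/(20·p₁(1−p₁)) + 1/(20·p₀(1−p₀))], and the CI factor each way is exp(1.96 × SE). At 10% vs 40%, SE = 1.236 and the factor is 11.3. At 20% vs 50%, SE = 1.012 and the factor is 7.3. The Firth values below come from simulation with 20 per cell.

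| Placebo vs Nyxol + LDP | Median Firth profile-CI factor each way | Chance that at least one placebo stratum has no responders, 1 − (1 − (1 − p₀)²⁰)² |
|---|---|---|
| 10% vs 40% | 12.9 | 23% |
| 15% vs 45% | 8.9 | 8% |
| 20% vs 50% | 7.3 | 2% |

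At a 5% placebo rate the empty-stratum chance is 59%. With an empty placebo stratum the median factor is about 50, but all Firth intervals stayed finite. Ordinary maximum likelihood has no finite estimate for such a cell, which is the reason for Firth.

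**5. Behaviour of the contrasts** (4,000 simulated trials per scenario). With no true iris difference, coverage of the Firth profile CI was 95% to 98%, and at least one of the two contrasts excluded no difference in 7% to 8% of trials. If the effect exists in only one stratum, the ratio-of-odds-ratios CI excludes 1 in 24% to 27% of trials. For the continuous contrast with a 0.73 SD effect in one stratum only, the figure is 37%.

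**6. Illustration: why within-stratum significance is not an answer.** Suppose the true effects are identical and the strata equal. Stratum power is p = Φ((1.96 + z)·√0.5 − 1.96), where z is the normal quantile of overall power. The chance that exactly one stratum is significant is 2p(1 − p).

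| Assumed overall power | p | Exactly one significant |
|---|---|---|
| 80% | 0.508 | 50% |
| 90% | 0.630 | 47% |
| 95% | 0.722 | 40% |
| 99% | 0.858 | 24% |

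**The case against.** The strongest reply is that nothing in the plan is wrong. The objective sets no hypothesis or test. Stratum odds ratios with CIs are a recognised descriptive way to look at a subgroup. Secondary p-values are descriptive, success rests on the overall PP analysis alone, and anyone could form a rough contrast from the reported stratum results. The added contrast will also be imprecise. All of this stands, and it keeps the severity modest. It does not remove the gap: a contrast formed afterwards is open to choice of scale and population, and a wide interval at least shows how little the trial can say about iris colour.

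Three stronger readings are tempting, and the documents do not support them.

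- A reader might infer that the plan would wrongly report an iris difference in 24% to 50% of trials. No SAP rule draws a conclusion from which stratum is significant, and the figures rest on assumed power. They are not an error rate of the plan.
- A reader might infer that no interaction is planned at all. The redacted code and table list prevent that claim, although the written models name only treatment, irides and baseline.
- A reader might want all iris conclusions confined to one or two new contrasts. That would demote iris results the SAP plans for pupil diameter, other timepoints and mITT.

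**Conclusion.** The gap holds for the readable text: the iris-colour objective has within-stratum results and main-effect adjustment, but no prespecified estimate with CI of the difference in effect. It is a cheap improvement of modest severity. No result is lost, and no stated estimate or decision rule is in error. The contrast would be imprecise: about 0.88 SD half-width on the continuous scale, and a factor of roughly 7 to 13 each way for the ratio of odds ratios, larger with an empty cell. These figures assume equal iris strata of about 20 per arm, and the ratio figures also assume the response rates shown. An unequal split or a smaller PP set would widen them.

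**What to change.** Add two contrasts for Nyxol + LDP versus Placebo alone, labelled exploratory. Each comes from the planned pooled model plus a treatment-by-irides term, in the PP population with observed cases. That matches the observed-case rule already set for the iris analysis of the primary endpoint. PP membership already requires that a subject "had binocular DCNVA and BCDVA in photopic conditions at Baseline (Visit 1) and at Visit 2 time 1 hour", so nothing needs imputing.

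1. **SAP 9.1.1, primary responder endpoint:** the ratio of odds ratios (dark versus light) with 95% CI, from Firth penalized logistic regression with a profile penalized-likelihood interval.
2. **SAP 9.1.2, change in binocular photopic DCNVA at 1 hour:** the difference in least-squares mean differences with 95% CI, from the ANCOVA.

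State that any claim that the effect on these two endpoints differs by iris colour will be judged from these contrasts and their CIs, not from which stratum reaches p ≤ 0.05. Keep every planned within-stratum result, including pupil diameter, other timepoints and mITT. Note that the pooled contrast, with one common baseline slope, need not equal the ratio of the separately fitted stratum odds ratios.

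The cost is SAP wording and two model fits, with no new data. The downside is wide intervals that cannot show absence of a difference, and a Firth interval that is somewhat conservative at low placebo rates.

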9.1.2. Secondary Efficacy Analyses

Secondary efficacy endpoints are indicated in Section 4.2.2. Secondary efficacy endpoints will be analyzed by study eye, fellow eye, and binocular (if available) using the PP population, and the mITT population for selected endpoints (see the list of planned tables, Section 12.1, for details).

All continuous secondary endpoints derived from VA assessments, such as change in DCNVA, DCIVA, and BCDVA, will be analyzed using Early Treatment Diabetic Retinopathy Study (ETDRS) letters correctly read. Any secondary endpoints using Snellen measurements will be converted from letters read as follows:

Table 2 Snellen Equivalents to VA Assessment Letters Read

DCNVA/DCIVA letters	Snellen	BCDVA letters
≥75	20/15	≥60
70 - 74	20/20	55 - 59
65 - 69	20/25	50 - 54
60 - 64	20/32	45 - 49
55 - 59	20/40	40 - 44
50 - 54	20/50	35 - 39
45 - 49	20/63	30 - 34
40 - 44	20/80	25 - 29
35 - 39	20/100	20 - 24
30 - 34	20/125	15 - 19
25 - 29	20/160	10 - 14
<25	20/200	<10

Each of the continuous secondary efficacy endpoints will be analyzed using analysis of covariance (ANCOVA), with observed value as the dependent variable, treatment, and light/dark irides as factors, and the respective baseline value included as the covariate. Another ANCOVA will be applied with change from baseline as the dependent variable using the same factors and covariates.

The output from each ANCOVA will include the LSM and SE for all treatment groups, along with each LSM, the 95% CI and associated p-value for Nyxol + LDP vs. Nyxol alone, Placebo + LDP, and Placebo alone. Continuous pupil diameter endpoints will be assessed using the study eye, fellow eye, and best eye, which is defined as the eye with the greatest reduction in diameter.

For each of the secondary endpoints related to percent of subjects achieving certain criteria, the analysis will be performed using a logistic regression model with treatment and light/dark irides as factors, and the respective baseline as a covariate. For each analysis, the percentage of subjects in each treatment group meeting the criteria will be presented, and the OR with 95% CI and p-value will be provided for Nyxol + LDP vs. Nyxol alone, Placebo + LDP, and Placebo alone. Categorical pupil diameter endpoints will be assessed using the study eye, fellow eye, and either eye, which is defined as achieving a given criterion in either eye.

In addition, each secondary efficacy endpoint will be analyzed by light/dark irides using the same model indicated above but without irides as a factor.

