## Measurements:

- DCNVA Reading/Near will be measured under photopic and mesopic conditions by a high-contrast Near Visual Acuity Chart in the [REDACTED] (Appendix 2)
- BCDVA will be measured under photopic conditions by a high-contrast Standard Early Treatment [REDACTED]  
[REDACTED]
- BCIVA will be measured under photopic conditions by a high-contrast Near Visual Acuity Chart in the [REDACTED] at [REDACTED]  
[REDACTED]
- PD will be measured with a [REDACTED] (mm)

All of the efficacy endpoints will be analyzed overall and by [REDACTED] at all timepoints. Subjects will also be analyzed by study eye, fellow eye, and binocular.

In photopic lighting conditions, [REDACTED] In mesopic conditions, [REDACTED] [REDACTED]. Ambient lighting [REDACTED]. The [REDACTED]. Subjects will be allowed to acclimate to these lighting conditions (with the eyes open [REDACTED] to the set of PD and VA measurements). Subjects will sit in the exam chair facing directly at the illuminated chart during the acclimation period and for all assessments.

[REDACTED] for the scheduled remaining safety assessments (e.g., conjunctival hyperemia, AEs, subject questionnaire, etc.). The subject will be in the same room for all assessments, and every effort will be made to have the same person perform the measurements at all visits.

For VA, measurements will be made in letters and will be converted to LogMAR and lines, as appropriate.

All of the efficacy endpoints will also be analyzed by Modified Intention-to-Treat (mITT) and Per Protocol (PP) populations.

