## 7. ASSESSMENT OF EFFICACY

### 7.1. *Specification of the Efficacy Parameters*

The primary efficacy endpoint is the percent of subjects with  $\geq 15$  letters of improvement in photopic binocular DCNVA on Visit 2 at 1 hour with Nyxol + LDP compared to Placebo alone. The improvement in binocular DCNVA for each subject is relative to the subject's own Baseline value (Visit 1).

Secondary efficacy endpoints, which will be assessed for the study eye, the fellow eye, and binocular can be found in [Section 4.1](#).

All of the efficacy endpoints will be analyzed overall and by light/dark irides at all timepoints.

All of the efficacy endpoints will also be analyzed by mITT and PP populations.

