## **9.2. Analysis Populations**

**Modified Intention-to-Treat:** The mITT population will include all randomized subjects who received at least one drop of Treatment 1 and were administered Treatment 2 (LDP or No Treatment). The mITT population will be used to analyze efficacy endpoints.

**Per Protocol Population:** The PP population included all subjects in the mITT who received one drop of Treatment 1 the day prior to Visit 2 and were administered Treatment 2 at Visit 2, had binocular DCNVA and BCDVA in photopic conditions at Baseline (Visit 1) and at Visit 2 time 1 hour, and had no major protocol deviations. The PP population will be used for the primary endpoint analysis and to analyze efficacy endpoints.

**All Randomized Population (ARP):** The ARP will include all randomized subjects. This population is also known as the Intention-to-Treat (ITT) population. The ARP will be used in confirmatory efficacy analyses.

**Safety Population (SP):** The SP will include all randomized subjects who have received at least one drop of study treatment (Treatment 1 or Treatment 2). The SP will be used to summarize safety variables.

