Each of the continuous secondary efficacy endpoints will be analyzed using analysis of covariance (ANCOVA) with change from Baseline as the dependent variable, treatment, and light/dark irides as factors, and the respective Baseline value included as the covariate. Each ANCOVA will be performed using the mITT and PP populations with subjects included in their randomized treatment regardless of the treatment they actually received. The output from each ANCOVA will include the least-squares mean (LSM) and standard error for all treatment groups, along with the placebo-corrected LSM for each treatment difference, its 95% CI, and associated p-value.

All continuous secondary endpoints derived from VA assessments, such as change in DCNVA, BCIVA, and BCDVA, will be analyzed using ETDRS letters correctly read.

For each of the secondary endpoints related to percent of subjects achieving certain criteria, the analysis will be performed using a logistic regression model with treatment, light/dark irides, and the respective Baseline as a covariate. For each analysis, the percentage of subjects in each treatment arm meeting the criteria, the OR with 95% CI and p-value will be provided. For these endpoints, the mITT and PP populations will be used with subjects included in their randomized treatment regardless of the treatment they actually received.

In addition, each secondary efficacy endpoint will be analyzed by [REDACTED] using the same model indicated above but without irides as a factor, as appropriate. Other subgroups, such as age, sex, and race, may be analyzed as well.

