3.3. Summary of Statistical Analysis Changes to the Protocol

The wording of the first secondary objective was changed from “< 1 line of loss” to “>1 line of loss”. An additional secondary endpoint for the percentage of subjects with distance-corrected near visual acuity (DCNVA) $\leq 20/15, \leq 20/20, \leq 20/25, \leq 20/32, \leq 20/40, \leq 20/50, \leq 20/63, \leq 20/80, \leq 20/100, \leq 20/125$, and $\leq 20/160$ was added to Section 4.2.2. The secondary endpoints originally specified as the percentage of subjects with improvement in best-corrected distance visual acuity (BCDVA) was changed to improvement or loss in BCDVA. The Snellen ranges for secondary endpoints with discrete ranges were changed to 25/50 to 20/63, 20/80 to 20/100, and 20/125 to 20/160. Otherwise, the analyses described in this analysis plan are consistent with the analyses described in the study protocol.

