7.1.1. Modified Intention-to-Treat (mITT)

The mITT population will include all randomized subjects who received at least one drop of Treatment 1 and were administered Treatment 2 (LDP or No Treatment). The mITT population will be used to analyze selected efficacy endpoints, with subjects included in their randomized treatment regardless of the treatment they actually received.

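### The SAP restricts the mITT analysis to selected secondary endpoints, contrary to the protocol and without declaring it, so any endpoint not selected has only a per-protocol efficacy analysis

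*SAP*

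**What the plan says.** **Protocol.** The commitment to both populations appears in several places.
- Section 4.1, under Measurements: "All of the efficacy endpoints will also be analyzed by Modified Intention-to-Treat (mITT) and Per Protocol (PP) populations".
- Section 7.1: "All of the efficacy endpoints will also be analyzed by mITT and PP populations".
- Section 9.2, on the use of mITT, with no restriction: "The mITT population will be used to analyze efficacy endpoints".
- Section 9.3.5, continuous secondary endpoints: "Each ANCOVA will be performed using the mITT and PP populations".
- Section 9.3.5, responder-type secondary endpoints: "For these endpoints, the mITT and PP populations will be used".

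**SAP.** Two sections narrow this.
- Section 7.1.1: "The mITT population will be used to analyze selected efficacy endpoints".
- Section 9.1.2: secondary endpoints are analysed "using the PP population, and the mITT population for selected endpoints", with a pointer to the planned tables in Section 12.1. That list is redacted in the public copy.

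SAP 7.1.2, by contrast, assigns PP to the primary endpoint and to all efficacy endpoints. SAP 3.3 lists four changes from the protocol: the wording of one objective, an added near-acuity endpoint, BCDVA improvement widened to improvement or loss, and revised Snellen ranges. It then states: "Otherwise, the analyses described in this analysis plan are consistent with the analyses described in the study protocol".

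**The concern.** On the choice of analysis set, the statement of consistency in SAP 3.3 is not correct. A reader who relies on that section would not learn that the broader population has been dropped for some secondary endpoints.

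The set that remains is a poor one to stand alone. PP membership is fixed by events after randomisation: taking Treatment 1 the day before Visit 2, having photopic binocular DCNVA and BCDVA at the 1-hour reading, and having no major deviation. The 1-hour requirement suits the primary endpoint. It has no bearing on a pupil diameter at 3 hours or a mesopic near acuity at 4 hours. For an endpoint analysed only in PP, usable readings are lost, and no broader analysis shows whether the result depends on who was removed.

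**Working it through.** The check is mainly a comparison of text.

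**1. Does the general rule in the SAP remove the conflict?** The opening of SAP 9 applies mITT and PP to efficacy unless otherwise noted. SAP 9.1.2 notes otherwise for secondary endpoints and SAP 7.1.1 agrees with it, so the general rule gives way. Two sections say the same thing, which makes a slip of wording unlikely.

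**2. Is the change declared?** None of the four changes in SAP 3.3 concerns the analysis population. It is not declared.

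**3. Does another planned analysis cover a non-selected endpoint?**
- Protocol 9.3.5 allowed ARP analyses with imputation for secondary endpoints if warranted.
- SAP 7.3.2.3 limits imputation to the primary endpoint. SAP 9 uses observed cases for secondary endpoints and describes the ARP confirmatory analysis for the primary endpoint only.
- SAP 10.8 runs photopic BCDVA gain or loss in the Safety Population. That is the one visible exception.

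**4. What does PP discard?** SAP 4.2.2 sets the PP conditions against endpoints that do not use the 1-hour acuities:
- photopic DCNVA, photopic BCDVA and pupil diameter at 30 minutes and at 2, 3, 4 and 6 hours;
- mesopic DCNVA at 2, 4 and 6 hours, with no 1-hour reading at all;
- two comparisons of Nyxol with Placebo at 0 minutes, before Treatment 2. Here PP membership depends on readings taken an hour later.

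Protocol 12.3 also gives equipment malfunction, with the pupillometer as its example, among major deviations. A device fault could therefore remove a subject's acuity data if the review judges it exclusionary.

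**5. Can the size be derived?** The plan gives no figure for PP exclusions. Its only attrition figure is 7%, used to inflate 140 evaluable subjects: 140 / (1 − 0.07) = 150.5, so 151, against about 152 stated. That figure reproduces within rounding, but it covers drop-out from Visit 1 to the end of Visit 2. Subjects lost before Treatment 2 leave mITT as well as PP, so 7% does not measure the gap between the two sets.

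**6. Illustration, with assumed counts.** 152 × 4/14 = 43.4, so about 43 subjects in each of the two larger arms. Assume that at an off-1-hour timepoint every subject has an observed value, with 15/43 responders on Nyxol + LDP and 8/43 on Placebo alone. Let PP exclude subjects from the active arm only.

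| Assumed exclusion | Active | Placebo | Difference |
|---|---|---|---|
| none | 15/43 = 34.9% | 18.6% | 16.3 points |
| 4 non-responders | 15/39 = 38.5% | 18.6% | 19.9 points |
| 6 non-responders | 15/37 = 40.5% | 18.6% | 21.9 points |
| 4 responders | 11/39 = 28.2% | 18.6% | 9.6 points |

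A handful of exclusions can move the estimate by several points in either direction. If excluded subjects respond like the rest of their arm, it does not move. The counts are assumptions, so the table shows sensitivity at this sample size and estimates nothing about this trial.

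**The case against.** The strongest reply is that the selection is not left open. SAP 9.1.2 refers to Section 12.1, which may name an mITT table for nearly every secondary endpoint. This stands as a limit on scope. A reader might infer that most secondary results, or specifically the component comparisons, the duration profile and the pupil endpoints, will come from PP alone. The visible text does not support that, because the list is redacted, and the redaction is not a fault of the plan. It does not answer the conflict itself: the protocol says all endpoints, the SAP says some, and SAP 3.3 reports no such change.

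A second reply is that mITT is not the randomised set either. It requires a drop of Treatment 1 and administration of Treatment 2, both after randomisation; the all-randomised set is the ARP. This is right. The contrast is between a broader and a narrower set, and restoring mITT would not give a full intention-to-treat analysis of the secondary endpoints.

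A third concerns size. A reader might compute that, with 5% to 15% of mITT excluded and all of them non-responders, a PP response of 50% overstates the mITT response by 2.5 to 7.5 points (50% × 0.95 = 47.5%; 50% × 0.85 = 42.5%). The documents do not support this as an estimate. The exclusion rate and the 50% are assumed, and nothing suggests that every excluded subject failed. Secondary analyses use observed cases, so a subject without a 1-hour acuity does not count as a failure for that acuity at 1 hour in mITT.

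There are real safeguards. SAP 8.2 settles deviation exclusions in masked review before database lock. SAP 7.4.1 makes secondary p-values descriptive. The primary endpoint keeps both mITT and PP, with imputation. These lower the stakes, but they do not recover readings lost to the 1-hour rule or the previous-day dose rule, and descriptive estimates and intervals can still be biased by selection.

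**Conclusion.** The point holds as an undeclared difference between protocol and SAP in the analysis set for secondary efficacy endpoints. It affects an unknown share of them. For each endpoint not selected for mITT, other than photopic BCDVA gain or loss, the only planned efficacy analysis is in PP. Valid readings away from 1 hour are then discarded, and selection bias is possible with no broader analysis to reveal it. The amount of bias cannot be derived from the documents.

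This should be corrected before unmasking. It does not touch the primary endpoint's success rule, and no formal claim hangs on a secondary result. The conclusion rests on the visible text of SAP 7.1.1, 9.1.2 and 3.3. If the redacted list gives every secondary endpoint an mITT table, the practical loss disappears and only the wording needs correcting.

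**What to change.** In SAP 7.1.1 and 9.1.2, state that the mITT population, observed cases, is used for all secondary efficacy endpoints alongside PP, as the protocol requires. Both sections must change, because editing 9.1.2 alone would leave 7.1.1 contradicting it. Bring the table list in Section 12.1 into line where needed.

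If the sponsor means to leave an endpoint out of mITT, name it in SAP 3.3 with the reason, before unmasking, and correct the statement that the analyses are otherwise consistent with the protocol.

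The cost is additional tables from the same programs, with no new data and no new model.
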